with instructions on how to minimize side effects including moving the site of nicotine patch placement each day and not repeating site of use for at least one week to minimize the risk of skin irritation. Also, participants will be instructed to remove the patch before bed if it significantly interferes with sleep. Finally, these materials will discuss anticipated negative consequences of dual use (nausea, headache) and advise participants to discontinue one or both products should they arise. To reduce the risks of medications being given to those other than study participants, we will instruct participants upon distribution of samples not to give medication to others. Medication packages will also have a sticker that says “for FreSH participant use only- do not distribute.” Medication comes in childproof packaging.

Our Data and Safety Monitoring Plan includes monitoring of Adverse Events (AEs). We will exclude patients based on standard FDA contraindications for NRT use (pregnancy, recent cardiovascular trauma). We will clearly advise against use of NRT during pregnancy and breastfeeding and will exclude patients who report that they are pregnant or breastfeeding. As part of routine dental visits, patients are asked about their pregnancy status, as some dental procedures and medications are contraindicated for pregnant women. A physician will be available throughout the study for consultation about AEs, etc. Participants will be instructed to discontinue use of the patch and/or lozenge entirely if a severe reaction develops. They will be encouraged to contact the research team (not their dentist) as soon as possible if they experience a SAE or if they have a reaction for which OTC labeling suggests seeing a provider. In the AAR training, dentists will get training on how to manage adverse events of NRT. However, for this study, participants and dentists will be advised that the study team, not the dentist, is responsible for managing study-related AEs. We will advise patients who have a study-related SAE to discontinue use of the study treatment (NRT or ET). Following any AEs or SAEs, if the study physician, the participant’s personal physician or the participant wishes it, the participant will be withdrawn from the study.

Risks of using NRT concurrently with cigarettes and/or other tobacco products

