6.5 Participant Withdrawal or Discontinuation from Study Procedures/Intervention

6.5.1 Reasons for Participant Withdrawal or Discontinuation from Study Procedures/Intervention

Participants are free to withdraw from participation in the study at any time upon request.

Participants may choose to discontinue the intervention or study procedure but continue to be followed.

Study sites could be closed by the PI if there are persistent problems with recruitment, or if study recruitment goals are met prior to the site completing recruitment.

6.5.2 Handling of Participant Withdrawals from Study or Participant Discontinuation of Study Intervention

Reasons for participant withdrawal will be documented on a dedicated Case Report Form.

Patient participants will be instructed by study staff to discontinue use of the patch and/or lozenge entirely if a severe reaction develops. They will be instructed to contact the study team (not their dentist) as soon as possible if they experience a SAE or if they have a reaction for which OTC labeling suggests seeing a provider. Practitioners will receive training on how to manage adverse events of NRT. However, for this study,

patient participants and practitioners will be advised that the study staff, not the practitioner, is responsible for managing study-related AEs. Patients who have a study-related SAE (as determined by the study PI and the IRB) will be advised to discontinue use of the study treatment (NRT or ET). All study related SAEs will be followed to resolution using a Case Report Form.

Power calculations and sample size estimates for this study account for 11% lost to follow-up/withdrawal. Thus, we will not replace subjects who withdraw unless attrition and withdrawal exceeds 11% of our planned study sample.

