10 ASSESSMENT OF SAFETY

10.1 Specification of Safety Parameters

Safety monitoring for this study will focus on Unanticipated Problems (UPs) involving risks to participants, including unanticipated problems that meet the definition of a serious adverse event. In addition, adverse events (AEs) including SAEs will be recorded, and the PI will monitor these events to grade severity, relationship to the study intervention, and assess whether the nature, severity, or frequency is unexpected. Any time a participant spontaneously reports (calls the study or the practitioner) an AE including SAE or UP, it will be recorded. Practitioners will be trained to direct any participants reporting AEs to Hennepin Healthcare study staff and will alert study staff of any reports of AEs. Adverse events to study medication will be queried at the 1-, 3-, and 6-month follow-up assessments.

Safety events will be recorded and reported into the National Dental PBRN safety event reporting system maintained by the NCC if the events are determined to be both unexpected and related to the study intervention. Study PI [name], will be informed via the safety event system when events are reported.

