10.3.1 Relationship to Study Intervention

To assess relationship of an event to study intervention the following guidelines are used:

1. Related (Possible, Probable, Definite)

- a. The event is known to occur with the study intervention, and/or
 - b. There is a temporal relationship between the intervention and event onset and/or
 - c. The event abates when the intervention is discontinued, and/or
 - d. The event reappears upon a re-challenge with the intervention.
2. Not Related (Unlikely, Not Related)
- a. There is no temporal relationship between the intervention and event onset, and/or
 - b. An alternate etiology has been established.

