10.3.2 Expectedness

The Study PI and/or study-appointed, clinically/medically responsible individual will determine whether an AE is expected or unexpected. An AE will be considered unexpected if the nature, severity, or frequency of the event is not consistent with the risk information previously described for the intervention.

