10.4 Reporting Procedures

10.4.1 Unanticipated Problem Reporting

Incidents or events that meet the OHRP criteria for unanticipated problems require the creation and completion of an unanticipated problem report form. OHRP recommends that investigators include the following information when reporting an adverse event, or any other incident, experience, or outcome as an unanticipated problem to the IRB:

- appropriate identifying information for the research protocol, such as the title, investigator's name, and the IRB project number;
- a detailed description of the adverse event, incident, experience, or outcome;

- an explanation of the basis for determining that the adverse event, incident, experience, or outcome represents an unanticipated problem;
- a description of any changes to the protocol or other corrective actions that have been taken or are proposed in response to the unanticipated problem.

To satisfy the requirement for prompt reporting, unanticipated problems will be reported using the following timeline:

- Unanticipated problems that are serious adverse events will be reported to the IRB within 1 week of the investigator becoming aware of the event.
- Any other unanticipated problem will be reported to the IRB within 2 weeks of the investigator becoming aware of the problem.
- All unanticipated problems should be reported to appropriate institutional officials (as required by an institution's written reporting procedures), the supporting agency head (or designee), and OHRP within one month of the IRB's receipt of the report of the problem from the investigator.

All unanticipated problems will be reported to NIDCR concurrently with reporting to the IRB. These reports will be made to NIDCR's centralized reporting system via Rho Product Safety:

- Product Safety Fax Line (US): [name]
- Product Safety Fax Line (International): [contact]
- Product Safety Email: [contact]

General questions about UP reporting can be directed to the Rho Product Safety Help Line (available 8:00AM – 5:00PM Eastern Time):

- US: [name]
- International: [contact]

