10.4.2 Serious Adverse Event Reporting

Any AE meeting the specified Serious Adverse Event criteria will be submitted on an SAE form to NIDCR's centralized safety system via Rho Product Safety. This report may be sent by fax or email. Once submitted, Rho Product Safety will send a confirmation email to the investigator within 1 business day. The investigator should contact Rho Product Safety if this confirmation is not received. This process applies to both initial and follow-up SAE reports.

SAE Reporting Contact Information:

- Product Safety Fax Line (US): [name]
- Product Safety Fax Line (International): [contact]
- Product Safety Email: [contact]

General questions about SAE reporting can be directed to the Rho Product Safety Help Line (available 8:00AM – 5:00PM Eastern Time):

- US: [name]
- International: [contact]

All SAEs will be followed until resolution or stabilization.

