11 STUDY OVERSIGHT

The principal investigator will be responsible for study oversight, including monitoring safety, ensuring that the study is conducted according to the protocol and ensuring data integrity. Study progress and safety will be reviewed monthly by the PI, when data will be reviewed for safety concerns and data trends. Reportable events that arise during the conduct of the study will be promptly submitted to the IRB. If necessary, additional steps may be taken to ensure data integrity and protocol compliance.

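### Section 6.5.2 makes the SAE-specific advice to stop study treatment depend on a relatedness determination by both the PI and the IRB, but the protocol describes no such IRB determination

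*Protocol*

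**What the plan says.** Section 6.5.2 contains two stop instructions. The first tells patients to stop the patch or lozenge altogether if a severe reaction develops, and it has no further condition. The second is specific to SAEs and covers both arms: "Patients who have a study-related SAE (as determined by the study PI and the IRB) will be advised to discontinue use" of the study treatment.

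Section 3.3.1 gives the SAE rule without saying who decides: "We will advise patients who have a study-related SAE to discontinue use of the study treatment (NRT or ET").

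The safety sections divide the work as follows:

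- Section 10.1: "the PI will monitor these events to grade severity, relationship to the study intervention".
- Section 10.3.1: "To assess relationship of an event to study intervention the following guidelines are used". Criteria follow, and no assessor is named.
- Section 10.3.2, on the neighbouring judgement of expectedness: "The Study PI and/or study-appointed, clinically/medically responsible individual will determine whether an AE is expected or unexpected".
- Section 10.4.1: "Unanticipated problems that are serious adverse events will be reported to the IRB within 1 week of the investigator becoming aware of the event".
- Section 10.4.2: "Any AE meeting the specified Serious Adverse Event criteria will be submitted on an SAE form". The form goes to the funder's safety system, and the IRB is not named.
- Section 11: "Reportable events that arise during the conduct of the study will be promptly submitted to the IRB". Which events are reportable is not defined there.

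**The concern.** A stop instruction after a serious event should rest on a judgement that the study team can make straight away. The parenthesis in section 6.5.2 joins the PI and the IRB with an *and*, so on its face the PI's own grading is not enough to trigger the advice. The protocol then gives staff no step by which to obtain the IRB's half of the decision and no time by which it would arrive. A coordinator following the sentence literally could hold back the advice for an SAE that the PI already regards as related.

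What is at stake is a safety action for individual patients. No estimate, test or power figure depends on it.

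**Working it through.** No arithmetic applies. The check sets the sections side by side.

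1. **The trigger.** Under section 6.5.2 the SAE-specific advice needs an SAE, and needs both the PI and the IRB to have determined it study-related. Section 3.3.1 needs only that it be study-related. One safety action is therefore stated twice, once with the condition and once without.

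2. **Who judges relatedness elsewhere.** Section 10.1 gives the grading to the PI. Section 10.3.1 supplies the criteria and mentions no IRB step. Section 10.3.2 shows that the companion judgement stays inside the study team. No section gives the IRB a relatedness decision to make.

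3. **What reaches the IRB, and when.** Two kinds of related SAE need separating.
   - *Related, unexpected, and suggesting greater risk than was known.* This meets all three criteria in section 10.1.1, so it is an unanticipated problem and goes to the IRB within 1 week under section 10.4.1. That is a limit on reporting. The protocol does not say that the IRB returns a ruling on relatedness, or by when.
   - *Related but expected.* This fails the first criterion in section 10.1.1, so it is not an unanticipated problem. Section 10.4.2 sends it to the funder's safety system. Section 10.4 gives no timed IRB report for it. It could fall within the undefined reportable events of section 11, but the text does not settle that.

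4. **What stop advice exists without an IRB ruling.**
   - *NRT arm.* Patients are told to stop on a severe reaction (sections 3.3.1 and 6.5.2). The printed materials advise stopping one or both products if nausea or headache from dual use arises (section 3.3.1).
   - *ET arm.* The severe-reaction instruction names only the patch and lozenge. The toothbrush is covered only by the SAE rule, which is conditional in section 6.5.2 and unconditioned in section 3.3.1.

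5. **Whether the severe-reaction instruction covers every SAE in the NRT arm.** It does not. Seriousness (section 10.1.3) and severity (section 10.3.3) are defined separately. A patient admitted to hospital may not see the event as a severe reaction to a patch or lozenge. For that patient the study team's advice is the backstop, and that is the advice carrying the condition.

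6. **Size.** A magnitude would need an IRB decision time and a rate of related SAEs. The protocol states neither, so none is computed.

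**The case against.** The strongest reply is that the sentence sets a minimum action and prohibits nothing. It says what will happen once an SAE is confirmed as related. It does not bar the PI from advising a patient to stop sooner. A physician is available for consultation throughout, patients are told to contact the study team after an SAE, and withdrawal at the wish of the participant, the study physician or the personal physician needs no IRB step (section 3.3.1). The parenthesis may be meant only as formal classification. How an IRB reaches a determination is usually set by that IRB, and IRB or network rules that are not shown may supply the missing route. The expected-SAE gap is also narrow: section 3.3.1 describes NRT risks as minimal and mild, so a related SAE would often count as unexpected in severity.

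Most of this stands, and it keeps the point minor. It also rules out stronger readings that a reader might infer:

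- *That section 6.5.2 confines all stop advice to SAEs ruled related by the PI and the IRB.* It does not. The severe-reaction instruction in the same section is unconditional.
- *That section 6.5.2 contradicts section 10.* PI grading followed by IRB review would satisfy both. Section 10.3.1 excludes nobody, and section 3.3.1 is silent on who decides.
- *That patients would go on using the product for some calculable period.* The 1-week figure in section 10.4.1 is a ceiling on reporting one class of event, and no delay in the advice can be derived from it.

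What the reply does not remove is the wording. The SAE sentence names the IRB as a joint decider, and the protocol shows no way to obtain that decision. The severe-reaction instruction does not reach the ET arm or every SAE in the NRT arm.

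**Conclusion.** The point holds as a narrow defect of wording in a safety instruction. Section 6.5.2 ties the SAE-specific stop advice to a joint PI-and-IRB determination that the rest of the protocol neither assigns to the IRB nor gives a route or time for.

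The practical effect is confined to SAEs that an NRT patient does not treat as a severe patch or lozenge reaction, and to SAEs in the ET arm. Such events are likely to be very few: the NRT is a two-week over-the-counter supply, and section 3.3.1 describes the toothbrush risks as minimal. No figure can be put on it. The primary outcome and its analysis are unaffected. Severity is minor.

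The conclusion assumes that staff would read the parenthesis as a condition on the advice, and that no IRB or network procedure outside the protocol already supplies a prompt ruling. If either assumption fails, the sentence is merely unclear, and the same edit is still worth making.

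**What to change.** In section 6.5.2, replace the parenthesis that names the PI and the IRB with: *as determined by the study PI or study physician under 10.3.1*. Then add one clause: *reporting to the IRB proceeds separately under 10.4 and does not delay this advice*. This brings the sentence into line with sections 3.3.1, 10.1 and 10.3.1 and leaves the IRB's reporting role as it is.

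The cost is a wording change to one sentence at the next amendment. It needs no added staff, visits or data.

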6.6 Premature Termination or Suspension of Study

This study may be suspended or prematurely terminated if there is sufficient reasonable cause. Written notification, documenting the reason for study suspension or termination, will be provided by the suspending or terminating party to the principal investigator. The principal investigator will also promptly inform the IRB and NIDCR and will provide the reason(s) for the termination or suspension.

Circumstances that may warrant termination include, but are not limited to:

- Determination of unexpected, significant, or unacceptable risk to participants.
- Insufficient adherence to protocol requirements.
- Data that are not sufficiently complete and/or evaluable.
- Determination of futility.

7 STUDY INTERVENTION

7.1 Study Product Description

Nicotine replacement therapy samples will include a 14-day supply of 14mg transdermal nicotine patches and a 14-day supply of 4mg nicotine lozenges.

Electric toothbrushes will be Sonicare brand. The toothbrushes will have the Seal of Approval from the American Dental Association.

7.1.1 Acquisition

Nicotine replacement therapy will be purchased directly from GlaxoSmithKline. If the NRT is out of stock at GlaxoSmithKline, then GlaxoSmithKline branded NRT will be purchased from an authorized retailer.

Electric toothbrushes will be purchased from a commercial vendor.

7.1.2 Formulation, Packaging, and Labeling

Transdermal nicotine patches, intended for 24-hour use, will be commercially packaged including FDA product insert. Packages include 14, 14mg patches.

Nicotine mini lozenges are intended for PRN use. The nicotine lozenges will contain 81 lozenges (a 2-week supply). Nicotine mini lozenges include the active ingredient of Nicotine polacrilex (equal to 4mg nicotine) and inactive Ingredients: Acesulfame potassiumcalcium polycarbophilflavorsmagnesium stearatemannitolpotassium bicarbonatesodium alginatesodium carbonatexanthan gum. The product is packaged for commercial sale and contains the FDA package insert.

Electric toothbrushes: N/A

7.1.3 Product Storage and Stability

Nicotine patches and lozenges are to be stored at room temperature away from excessive humidity.

Electric toothbrush: N/A

7.2 Dosage, Preparation and Administration of Study Product

Nicotine patches and lozenges do not require preparation. Nicotine patches are the 14mg strength, nicotine lozenges are the 4mg strength.

Electric toothbrushes: N/A

7.3 Accountability Procedures for the Study Product

Nicotine patches, lozenges and toothbrushes will arrive at Hennepin Healthcare. When they arrive, we will log their arrival and expiration date. We will document when they are mailed to the practice, the tracking number, and when they are received. Distribution will be measured via the patient after visit survey.

7.4 Study Behavioral Intervention Description

Practices will be randomly assigned to study condition (NRTS or ET). Practices will be instructed not to disclose the intervention condition to the patient participant until after the baseline survey has been completed.

AAR (both conditions): Practitioners (NRTS and ET) will be encouraged to deliver AAR to all patients regardless of trial participation.

Patient participants will receive:

- monogrammed study bag
- study trinkets such as pens and post-it notes
- a brochure published by the ADA describing the effects of tobacco use on oral and general health
- contact information for their state tobacco quitline
- information about tobacco cessation medications
- study contact information
- the follow-up schedule
- condition specific information about NRT/ET
- consent form
- HIPAA form

NRT sampling (NRTS): Practices assigned to NRTS will dispense NRT samples in addition to AAR.

Patient participants will receive: a “starter pack” consisting of a 2-week supply of both nicotine patches (14 mg) and lozenges (4 mg; combination NRT [C-NRT]). Practitioners will spend 1-3 minutes on instruction prior to dispensing samples. Instructions for NRT use are provided on each medication package. We will also include FAQs and information dispelling misconceptions. Practitioners will neither explicitly advise nor discourage combined use or concomitant use with cigarettes. Patients will receive oral and written instructions including how to obtain more nicotine replacement therapy if interested (e.g., from their primary care provider, or purchased over the counter). Practitioners will instruct patients that the samples are an opportunity for smokers to learn about two NRT products that can be used individually or together (participant choice, including none at all). Some suggested uses could be:

- to get experience with the products and determine if they like them
- to reduce smoking or restrict where they smoke

- to make a practice quit attempt
- to get started on quitting

Electric Toothbrush: ET practices will provide participants with an ET in addition to AAR. We selected ET to incentivize participation in usual care practices. ETs are more effective than manual toothbrushes at removing plaque and reducing gingivitis and gum bleeding. We will select an ET with the ADA seal of acceptance with a value similar to the NRT samples to equalize incentives and practitioner time across groups. Patients will receive instructions from the practitioner about how to use the ET.

7.5 Administration of Intervention

The intervention will take place in person during dental visits. Providers will ask all patients if they smoke, advise those who smoke to quit, and refer patients to the state quit line. Participants will then be given a sample (either nicotine replacement therapy or an electric toothbrush) and given brief use instructions. REDCap will automatically record the time it takes to give participants the intervention by timing the amount of time spent on each screen which displays the intervention script. Practitioners can opt out of having this information used for data analysis.

